**Table 3 - Sample Size Requirements by Size Effect**

ECC - A	ECC - B	Percent Difference (%)	Absolute Difference	Sample Size
4.00	4.40	10	0.40	81
4.00	4.44	11	0.44	67
4.00	4.48	12	0.48	57
4.00	4.52	13	0.52	49
4.00	4.56	14	0.56	43
4.00	4.60	15	0.60	37
4.00	4.64	16	0.64	33
4.00	4.68	17	0.68	30
4.00	4.72	18	0.72	27
4.00	4.76	19	0.76	24
4.00	4.80	20	0.80	22
4.00	4.84	21	0.84	20
4.00	4.88	22	0.88	19
4.00	4.92	23	0.92	17
4.00	4.96	24	0.96	16
4.00	5.00	25	1.00	15

Values are the mean change in bowel movement frequency (number of bowel movements per week) between baseline and Week 2. Higher values indicate a greater reduction in stool frequency.

Based on the above assumptions and assuming a 25% difference between treatments, a total sample size of 18 patients is recommended. It is expected that about 6 patients will be randomized at each of the 3 participating clinical sites.

With 18 patients, we will have more than 80% power to detect a minimal reduction in the weekly number of bowel movements by 4.

#### 14.2 Analysis Populations

- **The intent-to-treat (ITT) population** will include all randomized patients who complete the baseline evaluations, including those who are not exposed to study drug. The ITT population will be used for the primary analyses of all efficacy endpoints. Analysis will be done by randomized treatment.
- **The per-protocol (PP) population** will include all randomized patients who (i) are administered all study medication, in both study periods, in accordance with the protocol, including receipt of the two study drug doses in the randomized sequence, receipt of all dispensed study drug as described in the protocol, and non-use of medications prohibited by the protocol; (ii) have available information for the assessment of the primary endpoint, i.e. available weekly number of bowel movements at baseline and Week 2. The PP population will serve as the basis for secondary analyses of all efficacy endpoints.

For the purposes of identifying the PP analysis population, the protocol deviations/violations compiled during the study will be reviewed prior to database lock and, based on the PP definition above, will be classified as major vs. minor. Review of the relevant data available in the database will also be conducted to identify the patients to be included in the PP population.

- **The safety population** will include all randomized patients who received at least one dose of study drug treatment. This population will serve as the basis for analyses of all safety endpoints. Analysis will be done by actual treatment received.

### 14.3 Baseline and Demographic Characteristics

Demographic and baseline data will be summarized by treatment group using descriptive statistics. Demographics will include, among others, age, gender, ethnicity, weight, height, body mass index. Childbearing status and pregnancy test results will be summarized descriptively for each treatment group.

The demographics and baseline characteristics summary will be presented for the ITT and the PP populations to allow review of the characteristics of those included in the efficacy analyses.

#### Prior and Concomitant Medications

Medications used in this study will be coded by using the World Health Organization Drug Dictionary and categorized as follows:

- **Prior medication:** Any medication that started before the first dose of study drug, independently of when it ended.
- **Concomitant medication:** Medication continued or newly received at or after first dose of study drug to the last follow-up.

A given medication can be classified using the above, in one or more categories. If a medication has a missing or partial missing start/end date or time and it cannot be determined whether the medication was taken before the first dose of study drug or concomitantly, it will be considered as concomitant medication. Prior medications and concomitant medications will be summarized descriptively based on the ITT population.

### 14.4 Study Drug Exposure

The duration of study drug exposure is defined as follows: Last dose date minus first dose date plus 1 day, regardless of any interruptions in dosing. If the last dose date of study drug is missing, the patient's discontinuation or completion date will be used for analysis purpose. Duration of study drug exposure will be summarized descriptively as a continuous variable (number, mean, SD, median, minimum, and maximum), by study group, using the safety population.

### 14.5 Study Drug Compliance

Study drug compliance will be assessed at the end of each treatment period. Treatment compliance percentages will be summarized descriptively as continuous variables (number, mean, SD, median, minimum, and maximum) using the ITT and PP populations. The percentage of patients whose compliance is <80% or ≥80% will also be summarized, by study group.

## 14.6 Efficacy Analysis

### 14.6.1 Analysis of Primary Endpoint

For the primary objective of the study, descriptive statistics will be produced for the change in weekly frequency of bowel movements between baseline and the second week of treatment. A sequential analysis approach will be used where:

- a. First, the efficacy of the High ECC dose (4.25 g daily) will be tested using a paired Student's t-test and a null hypothesis of 0. If this comparison shows a statistically significant improvement, then the efficacy of the Low ECC dose will be tested.
- b. To assess the efficacy of Low ECC dose (1.7 g daily) a paired Student's t-test and a null hypothesis of 0 will be used, similarly to above. If this comparison shows a statistically significant improvement, then the two doses will be compared.
- c. To compare the efficacy of the two doses, the absolute change in weekly frequency of bowel movements will be compared using a paired Student's t-test and a null hypothesis of 0 ( $\delta_{\text{High}} - \delta_{\text{Low}} = 0$ ).
- d. Given the sequential design of the analysis correction for multiplicity will not be required.

If the change in weekly frequency of bowel movements between baseline and the second week of treatment does not follow the normal distribution the non-parametric Wilcoxon signed rank test will be used.

The primary analysis will be conducted on the ITT population. The PP population will be used in a secondary analysis.

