### **5.7 Study Rationale and Risk/Benefit Assessment**

The new ECC capsule has been developed to manage diarrhea associated with SBS. The formulation is expected to release cholestyramine in the remaining segment of the small intestine in SBS patients (mid-jejunum to terminal ileum), thus binding bile acids after fat digestion, but before induction of diarrhea in the colon. The delayed-release profile is also expected to help reduce the potential for DDIs occurring in the proximal small intestine.

Since delayed distal delivery of cholestyramine is expected to be more effective in prevention and reduction of diarrhea in SBS, compared to non-enteric coated cholestyramine powder, lower doses may be sufficient. The recommended adult dose of cholestyramine powder is 4 g, one to six times daily. Consequently, 2 doses of ECC were selected for this dose-finding study. The "high" dose will be 4.25 g (10 capsules) daily corresponding approximately to the recommended dose of cholestyramine powder. The "low" dose will be 1.7 g (4 capsules) daily. These doses will be evaluated for efficacy, safety, and tolerability in well-defined non fully colectomized SBS patients suffering from diarrhea.

To avoid any carry-over effect, a washout of 14 calendar days is planned between periods. Washout periods of a 7-14 day duration have been used in previous, published trials on cholestyramine and/or treatment of BAD.

The doses of ECC administered in this study are not anticipated to induce any potential risks to the patients and are well below the maximum doses of cholestyramine typically administered for other indications. The safety monitoring practices employed by this protocol (i.e. physical examination, vital signs, clinical laboratory assessments, and AE questioning) are adequate to protect the patients' safety and should detect all expected treatment-emergent AEs (TEAEs). The potential medical benefit from participation in this trial would be the expected reduction of diarrhea or bowel movements following treatment with "high" dose ECC, and potentially treatment with "low" dose ECC as well.

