## **6. STUDY OBJECTIVES**

### **6.1 Primary Objective**

The primary objective of this study is to investigate the clinical efficacy of new ECC capsules and select the most effective dose in adult patients with SBS.

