#### **14.1 Sample Size Determination**

This is a cross-over trial in which patients will be randomized to two different sequences of treatment.

The primary outcome measure will be the change in the weekly frequency of bowel movements between baseline and Week 2 of treatment (ie. Days 8 to 14, and Days 36 to 42). Efficacy will be assessed as the difference vs. baseline as well as the difference between the two treatments.

Given that this is a cross-over study, patient will serve as their own control and the statistical analysis will be based on matched comparisons. Depending on the distribution of the difference between the two treatments the parametric Paired Student's t-test, or non – parametric Wilcoxon's sign rank test will be used. The current sample size computation will be based on the parametric test, since this is more conservative and hence demanding of a higher sample size.

The following assumptions have been employed:

- i. The mean change in the lesser efficacious treatment will be 4 bowel movements per week.
- ii. The SD for the change in bowel movements per week will be 2.0 based on extrapolation of results from the literature (32).
- iii. The correlation of the changes between the two treatments will be 0.80 given that there is a strong patient effect on bowel movements. Hence the SD of the difference between treatment groups is 1.265 assuming an SD of 2.00 for each treatment group.
- iv. The significance level will be 0.05.
- v. The power of the study will be 80%.
- vi. The effect size to be detected will be between 10% and 25%.
- vii. Adjustment of 20% has been considered to compensate for attrition.

The following table describes the sample size requirements (number of patients) for the study by different effect size.

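### Making the High-versus-Low test wait for a significant Low result is not needed for error control, and it can block the dose comparison if Low's true effect is below about 2 per week

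*Combined protocol and SAP*

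**What the plan says.** Section 14.6.1 sets out three paired t-tests on the change in weekly bowel movements from baseline to the second treatment week: (a) High dose, (b) Low dose, (c) the difference between the doses. Each step opens only if the one before shows a significant improvement. For the last link the text reads: "If this comparison shows a statistically significant improvement, then the two doses will be compared". Item (d) adds: "Given the sequential design of the analysis correction for multiplicity will not be required". If the changes are not normally distributed, the fallback is a rank test: the change "does not follow the normal distribution the non-parametric Wilcoxon signed rank test will be used".

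Step (c) has a central place elsewhere. The primary objective (Section 6.1) is to "investigate the clinical efficacy of new ECC capsules and select the most effective dose in adult patients with SBS", and Section 7.1.1 makes the between-dose difference part of the primary endpoint assessment. Section 14.1 sizes the trial on it: "Based on the above assumptions and assuming a 25% difference between treatments, a total sample size of 18 patients is recommended". A second power statement there concerns change from baseline: "we will have more than 80% power to detect a minimal reduction in the weekly number of bowel movements by 4".

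On how well Low will work, the documents point different ways. Section 14.1 assumes: "The mean change in the lesser efficacious treatment will be 4 bowel movements per week". The dose justification in the Synopsis allows that the lower dose may do as well. Section 5.7 is more guarded and expects benefit "following treatment with 'high' dose ECC, and potentially treatment with 'low' dose ECC as well".

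**The concern.** Step (c) determines the 18 patients and is the only one of the three steps that compares randomised treatments. The other two are before-and-after comparisons without a control. Yet (c) comes last, behind a test that Table 3 does not size.

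If High is significant and Low is not, the plan allows no formal conclusion about High versus Low, however large the observed difference. One dose being significant and the other not is not a test of the difference between them. The trial could then meet a clear dose difference and have only descriptive statistics with which to report it. Two questions follow: does the Low gate buy any error control, and how often would it block step (c)?

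**Working it through.** **Inputs (Section 14.1).** SD of change 2.0 for each dose; correlation 0.80; alpha 0.05; power 80%; lesser dose 4 per week; difference 25% of 4 = 1.0 per week; 20% added for attrition. Sidedness is not stated. Two-sided is assumed here because it reproduces Table 3.

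**The plan's own figure.** SD of the difference = √(2 × 2.0² × (1 − 0.80)) = √1.6 = 1.265, as stated. With an exact noncentral t, two-sided 0.05, all 16 rows of Table 3 reproduce, from 81 down to 15. For the last row the noncentrality is 1.0 / (1.265/√15) = 3.06 and power is 81%. Then 15 × 1.2 = 18.

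The checks below use n = 15 (Table 3), n = 18 (no attrition) and n = 14 (18 × 0.8 = 14.4, rounded down).

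**Does the Low gate control error?** The three null hypotheses are High = 0, Low = 0 and High = Low.

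- If High = 0 is true, every false rejection must first pass step (a), which has level 5%.
- If High = 0 is false, Low = 0 and High = Low cannot both be true, since together they give High = 0. At most one true null remains, and it is tested at 5%.

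The gate on High therefore suffices. Simulation of the revised scheme with t-tests and complete data covered 9 null configurations × 3 correlations (0, 0.5, 0.8) × 3 sample sizes = 81 settings, with 100,000 trials each. The largest familywise error was 5.15% (simulation SE 0.07%), which is 5% within simulation error for a maximum over 81 settings. With each of 18 patients having a 20% chance of missing Period 2 completely at random, the maximum over 5 null configurations was 5.13% (SE 0.11%).

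**How often does the Low gate block step (c)?** The noncentrality of step (b) is Low / (2.0/√n). At n = 15 and Low = 2 it is 2 / 0.516 = 3.87, and power is 95%.

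| True Low effect per week | n = 14 | n = 15 | n = 18 |
|---|---|---|---|
| 4 | >99.9% | >99.9% | >99.9% |
| 2.0 | 93% | 95% | 98% |
| 1.5 | 74% | 77% | 85% |
| 1.0 | 41% | 44% | 52% |

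Step (b) reaches 95% power at a Low effect of 2.09, 2.00 and 1.80 per week (n = 14, 15, 18), and 80% power at 1.62, 1.56 and 1.40.

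**Chance of a significant step (c)**, as written / gated on High only (bivariate normal simulation; steps (a) and (b) must show improvement):

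| High / Low effect per week | n = 14 | n = 15 | n = 18 |
|---|---|---|---|
| 5 / 4 (planning case) | 78% / 78% | 81% / 81% | 88% / 88% |
| 4 / 2 | 93% / 100% | 95% / 100% | 98% / 100% |
| 3 / 2 | 72% / 78% | 77% / 81% | 86% / 88% |
| 4 / 1 | 41% / 100% | 44% / 100% | 52% / 100% |
| 2 / 1 | 29% / 74% | 33% / 78% | 44% / 87% |

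Only the first row uses the plan's effects. The others are assumed.

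**Sensitivity to the SD.** Section 14.1 extrapolates the SD of 2.0 from reference 32, a trial in diarrhea-predominant irritable bowel syndrome or functional diarrhea. The thresholds scale with the SD: at n = 15 the Low effect giving 95% power is about 3.0 per week for an assumed SD of 3, and about 4.0 for an assumed SD of 4.

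**The case against.** The strongest reply is that nothing is broken. Fixed-sequence testing is valid, item (d) is true as written, and at the plan's Low effect of 4 per week the gate costs nothing. Comparing doses only once both have shown an effect is a defensible choice in a proof-of-concept study, and with High significant and Low not, the sponsor would favour High anyway. All of this stands. What is lost is a formal conclusion, not the ability to choose a dose.

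The large losses also need a between-dose ratio well above the plan's 10% to 25%. If Low is weak and the 25% ratio is kept, step (c) has little power under either rule. At n = 15, High 2.5 / Low 2 gives about 27% as written against 29%, and High 1.25 / Low 1 gives about 3% against 9%. This stands too, although keeping the plan's absolute difference of 1.0 (the 3 / 2 and 2 / 1 rows) is an equally fair reading.

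The figure of 2 per week marks where blocking reaches about 5% at n = 15. Blocking reaches 20% only below about 1.4 to 1.6.

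Finally, the current rule needs only that each test has level 5%, whereas the revised rule also needs the logical link between the nulls. That link is exact for mean changes in the same patients, measured from baselines defined in the same way. It is approximate if some steps switch to the Wilcoxon test, or if patients missing a period enter (a) or (b) but not (c). Wilcoxon switching was not simulated. These are conditions to state in the plan; they do not undo the argument.

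**Conclusion.** The point holds as an improvement, not as an error. The Low gate is not needed for familywise error control. It is harmless at the plan's assumed effects, begins to block the dose comparison at a Low effect of about 2 per week, and blocks about half of trials at about 1 per week (step (b) power 41% to 52%). This rests on SD 2.0, correlation 0.80, two-sided 0.05 and normal data; a larger SD raises the thresholds in proportion. Low effects below 4 are assumptions, though Section 5.7 itself treats benefit from Low as uncertain. Since the comparison at risk is the one that sizes the trial and serves the primary objective, the change is worth making.

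**What to change.** In 14.6.1(b), delete the sentence that makes the dose comparison conditional on Low. Replace it with a rule to this effect: if step (a) is significant, steps (b) and (c) are each tested at two-sided 0.05, and neither depends on the other. Keep the gate on High; testing all three with no gate is not covered by the argument.

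In 14.6.1(d), give the reason: Low = 0 and High = Low together imply High = 0, so after step (a) at most one true null remains. Add that this is exact when all three steps test mean changes in the same patients from baselines defined in the same way, and approximate if some steps use the Wilcoxon test or different patients because of missing periods.

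The cost is one changed sentence and one added justification, with no new patients or data and no extra alpha under those conditions. The revised rule rejects everything the current rule rejects, and sometimes more. Section 14 allows the SAP to be amended until it is finalised before hard-lock. The change should be made and dated before any results by treatment are seen, and because the rule also stands in the protocol, it has to be classified as an amendment under Section 18.2.

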## 7.2 Study Overview

### 7.2.1 Study Design

This is a multiple center, randomized, double-blind, double dummy, 2-period, 2-sequence cross-over study design (Figure 1). The study will be conducted across three study centers. A total of 18 patients will be selected to participate in the study. All 18 patients will receive treatment with ECC during each study period. Patients will be randomized to either “low” dose ECC (1.7 g with matching placebo BID), or “high” dose ECC (4.25 g BID) daily for 14 days, followed by a 14-day washout, and then allocated to the other treatment for the second period.

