**Table 1 - Randomization**

	Period 1	Period 2
Sequence AB (n=9)	Treatment A	Treatment B

Sequence BA (n=9)	Treatment B	Treatment A
-------------------	-------------	-------------

JSS Medical Research will develop the computer-generated randomization sequences to be programmed into the Interactive Web Response System (IWRS), according to the study design, the number of subjects and the sequence of treatment administration. The IWRS will assign a randomization number to each patient. The random allocation of each sequence of drug administration to each subject is done in such a way that the study is balanced. Once generated, the randomization code will be final and will not be modified.

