### **8.6 Replacement of Patients**

A subject who withdraws during the pretrial evaluations but before receiving the treatment will not be considered as a drop-out and will not be included in the final statistical analysis.

Standbys should be recruited and available to replace any subject who withdraws prior to the first treatment administration.

Patients who are withdrawn or lost to follow-up during the study may be replaced in order to achieve the number of evaluable patients required, per the sample size calculations, to address the primary objective.

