## 12. EFFICACY ASSESSMENTS

### 12.1 Weekly Number of Bowel Movements

The total number of bowel movements (defecations) occurring during the second week of ECC treatment (Days 8 to 14) compared those occurring during screening in the week prior to randomization, will be used to assess the primary endpoint. Use of loperamide will also be recorded. Bowel movements will be recorded by the patients on a daily basis, as follows:

- each day of the last 14 days of the screening period, prior to randomization, to establish the first baseline and confirm subject eligibility
- each day of the first 14-day treatment period
- each day of the 14-day washout period
- each day of the second 14-day treatment period

[figure not shown]
In summary, this implies that occurrences of bowel movements will be recorded daily by the patient, in the diary, from Day -14 (screening) up to Day 42, i.e. the last dosing day of the study.

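### The High versus Low dose comparison ignores period and sequence in a randomised AB/BA cross-over, which costs power if there is a period effect and shifts the estimate if the sequences finish unequal

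*Combined protocol and SAP*

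**What the plan says.** Section 7.2.1 describes the trial: "This is a multiple center, randomized, double-blind, double dummy, 2-period, 2-sequence cross-over study design". Table 1 assigns nine patients to AB and nine to BA, and the text below it adds: "The random allocation of each sequence of drug administration to each subject is done in such a way that the study is balanced".

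The analysis does not use that structure. Section 14.1 states that "patient will serve as their own control and the statistical analysis will be based on matched comparisons", and sizes the trial on a paired t-test. Section 14.6.1 step c repeats it: "To compare the efficacy of the two doses, the absolute change in weekly frequency of bowel movements will be compared using a paired" Student's t-test against a null of zero. If the change "does not follow the normal distribution the non-parametric Wilcoxon signed rank test will be used".

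Three other places bear on the point:

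- Section 12.1 takes the screening week as the reference; the second-week count "compared those occurring during screening in the week prior to randomization, will be used to assess the primary endpoint".
- Section 5.7 justifies the 14-day washout by carry-over only.
- Section 8.6 makes replacement optional: "Patients who are withdrawn or lost to follow-up during the study may be replaced in order to achieve the number of evaluable patients required". It has no rule for restoring balance between sequences.

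Section 14 refers to a separate SAP. That is not among the documents, so this point concerns Section 14 as written.

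**The concern.** Step c is the only randomised contrast in the trial. Steps a and b test each dose against baseline, with no placebo arm. Step c also sets the sample size and serves the dose-selection part of the primary objective.

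In a two-period cross-over, anything that moves the outcome between the two second-week windows, which are four weeks apart, enters the High-minus-Low difference with opposite signs in the two sequences. A paired test pools the sequences and treats this systematic spread as random error, which widens the confidence interval and lowers power. If the sequences finish unequal, the opposite signs no longer cancel and part of the period effect is read as a dose effect. A washout guards against carry-over, which is a different problem.

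**Working it through.** **Inputs from the documents**

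- SD of change 2.0 per treatment and correlation 0.80 (Section 14.1), so the SD of the difference is 2.0 × √(2 × (1 − 0.80)) = 1.265.
- True difference 25% of 4.0 = 1.00 bowel movement per week (Table 3).
- Alpha 0.05. Sidedness is not stated; two-sided reproduces Table 3.
- Nine patients per sequence and 20% attrition.

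**Assumption.** Period effect p (Period 2 minus Period 1, on the reduction scale) from 0 to 2 bowel movements per week in either direction. The documents give no value.

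**The plan's own figure.** Exact noncentral-t power for a paired test with SD 1.265 gives n = 15 for a difference of 1.00 (81.2% power) and matches all 16 rows of Table 3. Then 15 × 1.2 = 18. This sizing contains no allowance for a period effect.

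**Model.** AB takes Low then High, so its High-minus-Low difference has mean tau + p. BA has mean tau − p. Within-sequence SD is σ = 1.265.

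- Paired estimate: the mean of all N differences, with expectation tau + p(nAB − nBA)/N.
- Expected sample variance in the paired test: σ² + p² × 4·nAB·nBA / [N(N − 1)]. At 9/9 and p = 1.0 this is 1.600 + 324/306 = 2.659, an SD of 1.63 in place of 1.265.
- Period-adjusted estimate: the average of the two sequence means, with standard error ½σ√(1/nAB + 1/nBA) and N − 2 degrees of freedom. It does not depend on p.

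**Power at 9/9, tau = 1.0** (200,000 simulated trials per cell)

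| p | Paired | Period-adjusted |
|---|---|---|
| 0 | 88.5% | 88.2% |
| 0.25 | 87.7% | 88.3% |
| 0.5 | 84.9% | 88.2% |
| 1.0 | 73.0% | 88.3% |
| 1.5 | 52.1% | 88.4% |

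The mean 95% confidence half-width at p = 1.0 is 0.80 paired and 0.62 adjusted. The signed rank test behaves alike: about 87% at p = 0 and 68% at p = 1.0.

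**Unequal completers.** If 3 of 18 drop out at random, the split is 8/7 with probability 2·C(9,1)·C(9,2)/C(18,3) = 648/816 = 0.79, and 9/6 with probability 168/816 = 0.21, counting both directions. With 4 dropouts, 7/7 has probability 0.42, 8/6 has 0.49 and 9/5 has 0.08.

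| Split (AB/BA) | p | Paired estimate | Paired power | Adjusted power |
|---|---|---|---|---|
| 8/7 | +0.5 | 1.03 | 79.3% | 80.6% |
| 8/7 | −0.5 | 0.97 | 73.4% | 80.6% |
| 8/7 | +1.0 | 1.07 | 68.6% | 80.6% |
| 8/7 | −1.0 | 0.93 | 55.0% | 80.6% |
| 7/7 | 1.0 | 1.00 | 58% | 77% |
| 9/6 | +1.0 | 1.20 | 81% | 79% |
| 9/6 | −1.0 | 0.80 | 41% | 79% |

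The apparent gain at 9/6 with p = +1.0 is bias, not information.

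**Type I error of the paired test at p = 1.0:** 1.3% (9/9), 1.5% (8/7), 3.1% (9/6), 4.9% (9/5). Across these splits and p from 0 to 2 it does not exceed about 5.1%. At 10/4, which would need unevenly allocated replacements, it is 10.9% at p = 1.0 and about 13% at p = 2.

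**The case against.** The strongest reply is that no period effect is documented and the design works against one. Entry requires stable diarrhoea for three months and through the screening diary, and permitted drugs must stay constant to Day 42. At 9/9 the loss is 0.6 points at p = 0.25 and 3.3 at p = 0.5, where the paired test still has 85% power, above the planned 80%. The large losses need p as big as the whole dose difference. This stands, and it is why the point is about efficiency. Even so, entry requires at least about 3 stools a day, or 21 a week, so p = 1.0 is under 5% of the lowest qualifying baseline (1/21 = 4.8%). The target difference is itself only 1.0. The Synopsis also lets the investigator change loperamide, which does not sit easily with Section 11.2.

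Two readings would shrink the loss:

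- **The SD may already contain period spread.** If 1.265 includes it, the paired test at 9/9 and p = 0.5 has about 90% power against 93% adjusted: a missed gain, not a fall below plan.
- **The baseline may be period-specific.** Section 12.1 calls screening the first baseline, and bowel movements are also recorded in washout. A washout baseline could absorb part of p. Section 14 defines baseline as the last measurement before the first dose, which favours a common one; a common baseline cancels in step c and leaves p in full.

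The imbalance figures also need perspective. Random dropout gives zero average bias over repeated trials; the harmful direction of 9/6 has probability about 0.10 given three dropouts; and at 8/7 the shift is only 0.07 at |p| = 1.0. Finally, a two-sample t-test on within-patient differences by sequence would be enough to remove the defect. That is correct: the mixed model is preferred because it also uses patients with one period.

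**Conclusion.** The concern holds. As written, step c analyses a trial randomised by sequence as if sequence and period did not exist. With nine completers per sequence the estimate is unbiased and the test is conservative, but power falls from about 88% to 85% at an assumed period effect of 0.5 bowel movements per week and to 73% at 1.0. With unequal completers the estimate in the trial actually run also moves by p(nAB − nBA)/N: 0.07 at 8/7, 0.20 at 9/6 and 0.29 at 9/5 for |p| = 1.0, in a direction set by the sign of p. Inflated false positives are not the main risk.

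These sizes rest on an assumed p, on 1.265 as the within-sequence SD, and on one common baseline. The case for change does not need a large p, because the adjusted analysis costs almost nothing in the likely splits. It should be fixed before database lock.

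**What to change.** Reword step c in Section 14.6.1, and carry it into the SAP:

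- **Primary analysis.** Linear mixed model on change in weekly bowel movement frequency from the common pre-randomisation baseline, with fixed treatment, period and sequence and a random patient effect. Use all randomised patients with at least one second-week value, and reconcile this with the ITT definition in Section 14.2. Name the degrees-of-freedom method; completers minus 2 was used in the check. Report the High-minus-Low difference with its 95% confidence interval.
- **Steps a and b.** If they are taken from this model, test the change-from-baseline least-squares means against zero, not raw counts.
- **Non-parametric version.** Rank-sum test on within-patient period differences by sequence, in place of the signed rank test.
- **Sensitivity analysis.** Keep the paired t-test.

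No new data are needed and the sample size need not change materially. If there is no period effect, the completer-only adjusted t-test loses 0.3 points of power at 9/9, 0.6 at 8/7, 2.0 at 9/6 and 4.1 at 9/5. The mixed model, using one-period patients as well, loses about 0.1 at 8/7 (81.1% vs 81.2%), 1.3 at 9/6 (79.9%) and 2.5 at 9/5 (75.6%). Its estimates were unbiased, with type I error of 4.7% to 5.2%. The rank-sum version costs more when p = 0 (83.7% vs 86.7% for signed rank at 9/9; 75.2% vs 79.3% at 8/7) but gains when p is large (83.6% vs 68.3% at 9/9, p = 1.0).
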